### **5.2.2 Timing of Dose Administration**

MK-8628 is to be administered orally with water in a fasted state, and as part of a BID regimen (twice daily, approximately 12±2 hours apart). The definition of a fasted state is that subjects should not have food for 1 hour before or 3 hours after study drug administration.

Dosing not performed at the same time (±2h) as on other days will be skipped. Subjects are to be instructed that if they vomit or skip their dose in that time frame, it is not to be replaced.

Capsules must not be opened or chewed.

A treatment cycle is 21 days (3 weeks). The subsequent cycle will begin on day 22 or after recovery from any AEs to baseline or Grade < 2 associated with the previous cycle.

Subjects should receive study treatment within 3 days following registration.

Details of the exact dose and time of administration will be documented in a validated subject diary and reported in the electronic case report form (eCRF).

#### **5.2.2.1 Premedication**

No systematic premedication will be given at least during the first cycle. See Section 5.5.1 for a list of allowed and prohibited medications

### **5.2.3 Trial Blinding**

This is an open-label trial; therefore, the Sponsor, investigator and subject will know the treatment administered.

### **5.3 Randomization or Treatment Allocation**

Cohort management and treatment allocation will occur centrally using an interactive web response system (IWRS). Subjects will be allocated to treatment by non-random assignment based on the open dosing cohort and number of available slots at the time of registration.

For NMC subjects, priority for treatment allocation will be to enroll into Part A of the study (Dose Escalation). If there are no slots available in Part A at the time the NMC subject is identified, the subject will be enrolled and allocated to treatment in Part B (NMC Cohort).

### **5.4 Stratification**

No stratification based on age, sex or other characteristics will be used in this trial.

### **5.5 Concomitant Medications/Vaccinations (Allowed & Prohibited)**

Medications or vaccinations specifically prohibited in the exclusion criteria are not allowed during the ongoing trial. If there is a clinical indication for any medication or vaccination specifically prohibited during the trial, discontinuation from trial therapy or vaccination may be required. The investigator should discuss any questions regarding this with the Sponsor Clinical Director. The final decision on any supportive therapy or vaccination rests with the investigator and/or the subject's primary physician. However, the decision to continue the subject on trial therapy or vaccination schedule requires the mutual agreement of the investigator, the Sponsor and the subject.

#### **5.5.1 Medications**

All treatments taken by subjects at study entry or within 4 weeks or 5 half-lives prior to initiating treatment (whichever is longer) or at any time during the study, in addition to the investigational product are considered concomitant medications and must be documented in the eCRF.

No premedication is planned.

#### **Allowed:**

- Supportive treatment of symptoms/AEs or standard treatment of concomitant conditions, including corticosteroids, aspirin, transfusion support, and antibiotics,
- Growth factors (Granulocyte-colony stimulating factor [G-CSF], erythropoietin [EPO] etc.) after cycle 1.
- For CRPC subjects, maintenance treatment with ongoing androgen deprivation therapy with a gonadotropin releasing hormone (GnRH) analogue or antagonist is mandatory providing serum testosterone is < 50 ng/dL (<1.7 nmol/L), unless the subject had previous bilateral orchiectomy as part of his hormone therapy.
- Chemotherapy, hormone therapy or any other anticancer therapy or surgical intervention resection performed  $\geq 3$  weeks prior to study start ( $\geq 6$  weeks for nitrosoureas or mitomycin C) or  $\geq 3$  half-lives for monoclonal antibodies or  $\geq 5$  half-lives for other non-cytotoxic agents (whichever is longer). Palliative radiation therapy (for analgesia) is authorized only if the irradiated field does not include target lesions.

- Bisphosphonates or denosumab given at stable doses for  $\geq 4$  weeks prior to study start. Bisphosphonates or denosumab are permitted from cycle 3.
- Prophylactic low-dose LMWH, as defined by local institutional practices; INR must be monitored in accordance with local institutional practices. Subjects who develop venous thromboembolic events during study requiring therapeutic levels of LMWH must be closely monitored for their platelet counts.

**Not allowed:**

- Other concurrent investigational drugs, agents or devices or any other therapy for cancer treatment.
- Any drugs given with a prophylactic intent during the first cycle.
- Concurrent treatment with strong CYP3A4 interfering drugs/substances is not permitted. The concomitant use of other CYP3A4 interfering drugs or any CYP2A6 interfering drug is allowed provided a careful follow-up of laboratory results that may be influenced by the concomitant agent is performed (e.g. INR if the concomitant agent is an anticoagulant, blood cell counts if the concomitant drug is hematotoxic must be followed up more frequently than required by the protocol).

Note: CYP3A4 inhibitors/inducers/substrates are listed in Section 12.6. Since this list is not comprehensive, the investigator should use his/her medical judgment when a subject presents with a medication not on the list or call the Sponsor Clinical Director for clarification.

- Use of therapeutic anticoagulation (e.g. warfarin, heparin, etc.). Must be stopped at least 7 days prior to the first dose of MK-8628.

## **5.6 Rescue Medications & Supportive Care**

No rescue or supportive medications are specified to be used in this trial.

### **5.6.1 Supportive Care Guidelines**

Toxicities will be managed by the investigator according to the local standard of care, except where noted in this protocol. Supportive treatment must be reported in the concomitant medication section of the eCRF.

#### **5.6.1.1 General Guidelines for Clinically Significant Toxicities**

General guidelines regarding management and dose reduction for adverse events that are considered by the investigator to be related to study treatment are provided in Section 5.2.1.6. All adverse events should be monitored closely, with supportive care provided according to institutional standards.

### **5.6.1.2 Hepatic Laboratory Abnormalities**

All trial subjects with liver test abnormalities should be monitored weekly until all abnormalities return to normal or to the baseline state. For subjects with isolated total bilirubin increases >2X ULN or 2X baseline (if elevated at baseline), monitoring should be every 2 weeks until bilirubin returns to normal or to the baseline state. Drug induced liver injury (DILI) may develop or progress even after the causative drug has been stopped. Results should be recorded on the case report form and in the database. See Section 12.7 for guidelines on the handling of these events (potential Hy's law cases).

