### 5.2.1.6 Dose Adaptation

The Common Terminology Criteria for Adverse Events version 4.0 (CTCAE 4.0) must be used to grade the severity of adverse events. MK-8628 will be withheld for drug related Grade 4 hematologic toxicities, non-hematological toxicity  $\geq$  Grade 3 including laboratory abnormalities, and severe or life-threatening AEs as per [Table 7](#) below. If a dose of MK-8628 is withheld for toxicity, then subjects may resume dosing with MK-8628 if that is appropriate at their next scheduled appointment or when toxicity has improved as described below.

Table 7: Dose Modification Guidelines for Drug-Related Adverse Events

Toxicity	Grade	Hold Treatment (Y/N)	Timing for restarting treatment	Dose/Schedule for restarting treatment	Criteria for discontinuation after consultation with Sponsor
Hematologic toxicity	1, 2	No	N/A	N/A	N/A
	3 associated neutropenia with infection; or thrombocytopenia with bleeding or lasting > 7 days	Yes	Toxicity resolves to Grade 0-1, or to baseline	Resume treatment at next lower dose level ( Table 8 )	Toxicity does not resolve within 2 weeks of last dose. Permanent discontinuation should be considered for any severe or life-threatening event
	4 or febrile neutropenia	Yes	Toxicity resolves to Grade 0-1, or to baseline	Resume treatment at next lower dose level ( Table 8 )	Toxicity does not resolve within 2 weeks of last dose. Permanent discontinuation should be considered for any severe or life-threatening event
Non-Hematologic	1, 2	No	N/A	N/A	N/A

Toxicity	Grade	Hold Treatment (Y/N)	Timing for restarting treatment	Dose/Schedule for restarting treatment	Criteria for discontinuation after consultation with Sponsor
Laboratory Abnormalities	3, 4  With or without symptoms lasting > 48 hours	Consider holding  Hold treatment for total bilirubin increases >2X ULN or 2X baseline (if elevated at baseline) and/or AST or ALT ≥ 5X ULN	Toxicity resolves to Grade 0-1, or to baseline	Laboratory abnormalities resolve within 1 week: treat at same dose and schedule  Laboratory abnormalities do not resolve within 1 week: may consider resuming treatment at next lower dose level (Table 8)	Toxicity does not resolve within 2 weeks of last dose. Permanent discontinuation should be considered for any severe or life-threatening event
Non-Hematologic toxicity	1 2	No	N/A	N/A	N/A

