- e. Radiologic exams (CT, MRI, chest X-ray) performed as part of the subject's standard follow-up within 4 weeks prior to the first treatment cycle, are acceptable. Radiologic assessment will be performed every 2 cycles (6 weeks) ( $\pm$  3 days) as per RECIST 1.1 or PCWG2 until progression, by calendar date starting from Cycle 1 Day 1 (not adjusted for cycle or treatment days). Scans used for tumor measurements may be requested for central review;
- f. Bone scans are mandatory in CRPC subjects and will be performed every 4 cycles (12 weeks) ( $\pm$  3 days) until progression, by calendar date starting from Cycle 1 Day 1 (not adjusted for cycle or treatment days). Scans used may be requested for central review;
- g. Record all AEs occurring within 30 days after the last dose of trial treatment regardless when the Treatment Discontinuation Visit occurs. After 30 days, any drug related AE regardless of seriousness occurring outside of any reporting timeframes must be reported;
- h. From Cycle 3 on, in the absence of  $\geq$  grade 2 abnormalities, these tests will be performed every cycle on Day 1, otherwise they are to be done weekly until resolution to baseline levels or  $<$  grade 2;
- i. Screening CBC and serum chemistry measurements must be taken within 7 days of the first dose of study treatment; All laboratory assessments (e.g. CBC, serum chemistry, PT [INR], aPTT, Factor VII, and PSA [if applicable]) on Cycle 1 Day 1 must be taken prior to the first dose;
- j. From Cycle 3 on, in the absence of  $\geq$  grade 2 abnormalities requiring weekly CBC and serum chemistry measurements, these visits may be conducted via a documented telephone contact with the Investigator or Sub-Investigator. Adverse events and concomitant medications will be reviewed; blood tests and vital signs will not be required;
- k. For women of reproductive potential, urine pregnancy test must be confirmed negative within 72 hours prior to receiving the first dose of study medication. If the urine test is positive or cannot be confirmed as negative, a serum pregnancy test will be required. The subject must be excluded in the event of a positive or borderline-positive serum test result;
- l. As appropriate for tumor type; For CRPC subjects, Prostate Specific Antigen (PSA) measurements are mandatory, and will be performed at screening, and then on Day 1 of every cycle starting with Cycle 2;;

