- m. Pharmacokinetics will be performed in cycle 1 only. Samples will be collected immediately prior to the first dose (T0) on day 1, 20min $\pm$ 5min, 1h $\pm$ 10min, 2h15min $\pm$ 10min, 3h15min $\pm$ 10min, 8h $\pm$ 1h, and 12h $\pm$ 2h post-dose (immediately before the second daily dose on day 1);
- n. Steady-state PK blood samples will be collected on days 8 ( $\pm$ 1 days) and 15 ( $\pm$ 2 days) of cycle 1, and day 8 ( $\pm$ 1 days) of cycle 2 (day 22,  $\pm$ 3 days), prior to the morning drug intake;
- o. PD blood samples will be collected immediately prior to the first dose on day 1, 3h15min $\pm$ 10min, 8h $\pm$ 1h and 12h $\pm$ 2h post-dose, and immediately prior to the first dose on day 8 only;
- p. Blood for Genetic Analysis samples should be collected prior to the first dose only at Cycle 1 Day 1. Details for collection can be found in Section 7.1.3.3.
- q. During the treatment phase, the assessment schedule for scheduled visits, collection of blood for labs, and other study procedures should be held/delayed to correspond with any dose hold – in other words, study visits and assessments coincide with the dosing calendar (cycle/treatment day), not the actual calendar. There is one notable exception to this – radiologic scans for tumor assessments (including bone scans and PSA measurements) should be conducted every 6 weeks (or 12 weeks for bone scan/PSA) by calendar date starting from Cycle 1 Day 1.

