### **12.7.3 Close Observation Recommendations**

The following steps should be taken when a subject is observed to have an elevated AST or ALT lab value that is greater than or equal to 3X ULN and an elevated TBL lab value that is greater than or equal to 2X ULN and, at the same time, an ALP lab value that is less than 2X ULN, as a result of within-protocol-specific testing or unscheduled testing. In addition, close monitoring of *isolated* bilirubin increases greater than 2X ULN will be required.

Initiate **close observation**, defined below, and continue performing **follow-up to resolution**.

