**Close observation is defined as follows:**

- Repeat liver enzyme and serum bilirubin tests two (2) or three (3) times weekly. Frequency of retesting can decrease to once a week or less if abnormalities stabilize or study drug has been discontinued and the subject is asymptomatic.
  - For subjects with *isolated* bilirubin elevations greater than 2X ULN, repeat serum bilirubin tests every 2 weeks until the bilirubin returns to normal or baseline.
- Obtain a more detailed history of symptoms and prior or concurrent diseases. (See Section 12.7.5).
- Obtain a history of concomitant medication use (including prescription and nonprescription medications, herbal and other dietary supplements), alcohol use, recreational drug use and special diets. (See Section 12.7.5 for details.)
- Obtain a history of exposure to chemical agents or other environmental toxins.

- Obtain additional history and complete Stage 1 work-up to attempt to rule out other potential causes of the transaminase elevation, including but not limited to the following: acute viral hepatitis types A, B, C, D, and E; autoimmune or alcoholic hepatitis; non-alcoholic steatohepatitis (NASH); hypoxic/ischemic hepatopathy; and biliary tract disease. (See Section 12.7.5.5 for details.)
- Consider gastroenterology or hepatology consultation.

**In general, treatment with study therapy should be stopped if the laboratory criteria for potential DILI are met. Please refer to the specific discontinuation criteria in the protocol as appropriate.**

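### During a Cycle 1-2 dose hold for isolated bilirubin above 2X ULN, the stated minimum retest interval is 2 weeks, too long to show whether Table 7's 1-week resolution condition was met

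*Combined protocol and SAP*

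**What the plan says.** **Monitoring.** Section 5.6.1.2 opens with weekly monitoring for liver test abnormalities in general and then makes an exception: "For subjects with isolated total bilirubin increases >2X ULN or 2X baseline (if elevated at baseline), monitoring should be every 2 weeks". Section 12.7.3 states that close monitoring of isolated "bilirubin increases greater than 2X ULN will be required", and its definition of close observation tells sites, for this group, to "repeat serum bilirubin tests every 2 weeks until the bilirubin returns to normal or baseline".

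**Hold and restart.** Table 7 in Section 5.2.1.6, in the Grade 3, 4 row for non-hematologic laboratory abnormalities, says: "Hold treatment for total bilirubin increases >2X ULN or 2X baseline (if elevated at baseline) and/or AST or ALT" at or above 5X ULN. The restart rule is "Laboratory abnormalities resolve within 1 week: treat at same dose and schedule". If resolution takes longer, the next lower dose may be considered. The criterion for discontinuation, after consultation with the Sponsor, is "Toxicity does not resolve within 2 weeks of last dose". The text after Table 8 adds that an interruption of more than 2 weeks for toxicity ends treatment unless the Sponsor agrees otherwise.

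**Scheduled chemistry.** The Section 6.0 flow chart has serum chemistry on Days 1, 8 and 15 of Cycles 1 and 2. Footnote q says that scheduled visits, "collection of blood for labs, and other study procedures should be held/delayed to correspond with any dose hold". Its only stated exception is tumor scans, bone scans and PSA. Footnote h applies from Cycle 3: chemistry on Day 1 of each cycle if there is no abnormality of Grade 2 or higher, "otherwise they are to be done weekly until resolution to baseline levels" or below Grade 2.

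**DLT definition.** Under Section 5.2.1.4, a drug-related Grade 3 or 4 non-hematologic laboratory abnormality in Cycle 1 is a DLT if, among other grounds, it lasts more than 1 week.

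**The concern.** The rule that holds the drug and the rule that retests the subject use the same bilirubin threshold, but their time scales do not match. Table 7 needs to know what happened by 1 week; the required test comes at 2 weeks. A site can follow the stated schedule in full and still lack the result that Table 7 asks for.

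Two features suggest that this was not intended. The same Table 7 cell also holds drug for raised AST or ALT, and that hold gets weekly tests under the general sentence of Section 5.6.1.2, so the 1-week rule works there. And, read literally, Section 5.6.1.2 tests an isolated bilirubin rise at or below 2X ULN weekly, but a larger one only every 2 weeks.

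At stake is consistent restart dosing across sites in both parts of the trial, and avoidable pressure on the 2-week limit. In Part A Cycle 1, a DLT classification may also be affected. One DLT matters to the escalation rule: in Table 5 with 6 subjects, going from 0 to 1 DLT changes the action from escalate to stay, and going from 2 to 3 changes it from stay to de-escalate.

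**Working it through.** The plan has no figure to reproduce here. The check sets the stated intervals side by side.

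**1. Which stated tests apply during a hold in Cycles 1-2?**

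| Source | Interval | Applies? |
|---|---|---|
| 5.6.1.2, general sentence | Weekly | No, on the natural reading: the next sentence gives isolated bilirubin its own interval |
| 5.6.1.2 exception, and 12.7.3 | 2 weeks | Yes |
| 12.7.3, main close-observation rule | 2 or 3 times a week | No: set for combined transaminase and bilirubin elevation; isolated bilirubin has its own sub-item |
| Flow chart, Days 1, 8 and 15 | About weekly | No: delayed by footnote q |
| Footnote h | Weekly if Grade 2 or higher | No: starts at Cycle 3 |
| 7.1, unscheduled tests | None stated | Allowed, not required |

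The Hepatic Assessment Flow Chart (Figure 5) is not reproduced in the available text, so the statement covers the text only.

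**2. What can the required tests show?** Let day 0 be the day the rise is detected and drug is held, and start the 1-week clock there. Table 7 does not state its start, so this is an assumption.

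- Tests at days 0 and 14 place recovery somewhere in the interval (0, 14]. The cut-off, day 7, lies inside it.
- Normal at day 14: recovery on days 1-7 (same-dose branch) and on days 8-14 (lower-dose-may-be-considered branch) look identical.
- Still raised at day 14: the abnormality has not resolved, but the discontinuation criterion has then been reached.
- So whenever the subject is fit to restart on the day-14 result, that result does not identify the branch.

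**3. With a weekly test.** Tests at days 0, 7 and 14 split the interval into (0, 7] and (7, 14], exactly at the cut-off. Required tests after day 0 and up to the cut-off: 0 at the 2-week interval, 1 at the weekly interval.

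**4. The 2-week limit.** A retest at day 14 leaves no slack. If the visit or the result is 1 day late, the interruption is 14 + 1 = 15 days, over the limit, and continuing then needs Sponsor agreement.

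**5. The DLT limb.** Its cut-off is also 1 week. By step 2, a normal day-14 result cannot show whether a related Grade 3-4 rise lasted more than 7 days. This matters only if no other DLT criterion has already settled the case.

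**The case against.** **Earlier testing is open to sites, and other text encourages it.** Section 7.1 allows unscheduled tests, Section 5.6.1.1 asks for close monitoring of adverse events, and Section 5.2.1.6 lets dosing resume once toxicity has improved. Bilirubin at or above 2X ULN is an event of clinical interest whose follow-up is reported within 24 hours, and grade changes and stop dates must be recorded. A site that holds drug under a 1-week rule has an obvious reason to test at 1 week. All this stands and lowers the likely harm. None of it sets an interval, and for this group Section 12.7.3 defines close monitoring as a test every 2 weeks.

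**The restart dose is not decided by the 1-week result.** A reader might infer that an unclassifiable day-14 result produces a wrong dose. The documents do not support that. The slower branch only permits a lower dose, so the same dose is open in both. A general sentence after Table 7 speaks of resuming one level down, but the row is more specific. For subjects on 10 mg BID no reduction is allowed, so the dose question does not arise.

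**Footnotes q and h might be read differently.** If q also suspends the weekly tests in h, the gap extends beyond Cycle 2. The narrower reading, Cycles 1-2, is used here.

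**The evidence that isolated rises will occur is indirect.** Section 4.2.2 lists asymptomatic bilirubin increases among the main dose-limiting toxicities in hematologic malignancies, but asymptomatic does not mean isolated. In the solid-tumor study (Section 4.1.3), the one hepatic DLT among 16 subjects on 80 mg QD continuous was combined with transaminitis. This objection stands.

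**Conclusion.** The mismatch is real: two stated rules use the same bilirubin threshold, and the required test cannot supply the result that the restart rule calls for. It is confined to isolated bilirubin above 2X ULN or 2X baseline, drug held, Cycles 1-2, and no discretionary test. It rests on reading the 2-week sentence as an exception to the weekly one, and on footnote q suspending scheduled chemistry. The DLT consequence is narrower still: Part A, Cycle 1, drug-related and Grade 3-4. The documents do not say that bilirubin above 2X ULN is Grade 3, so many held subjects may fall outside it.

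The documents give no frequency or recovery times for isolated rises, so neither the number of subjects affected nor a misclassification rate can be calculated. The point is minor to moderate, and worth correcting because the correction is cheap.

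A reader might also infer that the 2-week retest pushes subjects over the missed-dose DLT criterion. The documents do not support that as a consequence of this interval. They allow restart before the scheduled retest, they do not settle whether held doses count as missed or only postponed, and a hold of a full week could meet that criterion even with weekly testing.

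**What to change.** In Sections 5.6.1.2 and 12.7.3, require total bilirubin with ALT, AST and ALP at least weekly by calendar date, including about day 7, while drug is held for isolated bilirubin. The added enzymes show whether the rise is still isolated. In footnote q, exempt these tests from the delay that goes with a dose hold. The 2-week interval may stay for subjects who are not on a hold.

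This is about one line in each of three places. The downside is a few extra local blood draws and visits in the affected subjects.
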